We conducted a first clinical trial at Unit 72 Addictology of CHU Brugmann between 2017 and 2020 (reference: CE 2017/117), which was funded by the King Baudouin Foundation (ref: 2016-J1130650-206500) and then by the Brugmann Foundation (fund 2020-2021) (article in writing, pre-registered: <https://clinicaltrials.gov/ct2/show/NCT03447054>). The study had a design with 2x2 conditions combining 5 sessions of (A) tDCS on the dlPFC (anode on the right and cathode on the left, active 2mA vs sham 0mA) simultaneously to (B) an inhibition cognitive training (ICT) type Go/Nogo (specific vs non-specific). The specific ICT consisted to associate the Nogo with alcohol images and Go with sports images. There were also neutral images associated with 50% of Go. While non-specific training had only neutral images. Results showed a decrease in relapse's rate two weeks after treatment due to real tDCS combined with ICT. Moreover, we found out that real tDCS combined with specific ICT was more effective than real tDCS combined nonspecific ICT. Nevertheless, we did not find any significant effect on other clinical variables [craving (visual analog scale), symptoms of depression (BDI-II), anxiety (STAI-A), work memory (OSPA) and inhibition (Stop signal task)].

Following these results, one question still remains: Should tDCS be combined with ICT in order to be effective? To answer this question, we are conducting a new clinical trial with 5 sessions of tDCS on CPFDL (20minutes, anode on the right, left cathode) without an ICT. This study follows the same tDCS configuration as the previous one and takes place within the same multidisciplinary framework of treatment in order to compare our data.

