3.5. Statistical analyses

Primary measurement: In order to respond to our primary assumptions about relapse, we will perform logistic regressions with the independent variable conditions (tDCS active scored 1 and tDCS sham scored -1) and the variable dependent relapse at each measurement (2 weeks, 1 month, 3 months, 6 months and 1 year). A Kaplan-Meier survival analysis will be performed on the number of days prior to relapse to compare the curves up to one year of follow-up.

Finally, in order to compare our two conditions to the four conditions of the previous study, we will perform a logistic regression with linear polynomial contrasts (combined active tDCS with ICT > tDCS only > tDCS sham).

Secondary measures: In order to respond to our secondary assumptions about the variables before and after the intervention, we will perform mixed repeated measures ANOVAs [Time (T1 vs. T2) x Condition (tDCS active vs. tDCS sham)].

4. Benefits

At the individual level, stimulation by tDCS could on the one hand help patients to prolong alcohol abstinence time and on the other have positive effects on mood, especially an improvement in the level of anxiety and depression.

In a broader sense, this study will contribute to a better definition of the mechanisms involved in abstinence and in the phenomenon of relapse of alcohol use disorders. It will also compare whether tDCS is more effective alone or combined with cognitive training. The purpose of this study is to support medical research to improve management for people with alcohol dependence.

5. Safety and tolerability of tDCS

The tolerance of tDCS will be assessed during stimulation with an likert scale. A short questionnaire reporting possible side effects will be distributed to all participants to record the symptoms caused by stimulation.

The most common side effects include tingling, itching, and mild erythema. Although they are less frequent, the perception of a feeling of discomfort or burning, as well as the occurrence of a headache, are also possible events. These are side effects that are well tolerated, essentially limited to the time of stimulation and do not require medical treatment. Severe adverse effects or late onset were not identified.

6. Ethics

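### The linear polynomial contrast cannot test tDCS alone against tDCS plus ICT, as Section 4 promises; on the three named levels it is in effect combined versus sham

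*Combined protocol and SAP*

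**What the plan says.** Section 1 closes its account of the previous study with the question that motivates this one: "Should tDCS be combined with ICT in order to be effective". The new trial gives tDCS without inhibition cognitive training (ICT), so data on the combination can come only from the earlier study. Section 1 describes that study: "The study had a design with 2x2 conditions combining 5 sessions of (A) tDCS on the dlPFC", crossed with specific or non-specific ICT. Every earlier arm, sham included, therefore received some ICT. Section 1 also reports that "real tDCS combined with specific ICT was more effective than real tDCS combined nonspecific ICT".

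Section 3.5 sets out the cross-study step "in order to compare our two conditions to the four conditions of the previous study" and specifies it in one clause: "we will perform a logistic regression with linear polynomial contrasts (combined active tDCS with ICT > tDCS only > tDCS sham". It gives no contrast weights, quadratic term, pairwise contrast or study term, and no rule for turning six conditions into three levels. The other relapse analyses compare active with sham tDCS inside the new trial.

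Section 4 then states: "It will also compare whether tDCS is more effective alone or combined with cognitive training".

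**The concern.** A linear trend test over ordered groups asks whether the outcome changes from one end to the other. Section 4 asks something different: whether the upper step, from tDCS alone to tDCS plus ICT, is there at all. A significant trend can come entirely from the gap between combined and sham, wherever the middle group lies.

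The risk is that a significant result is reported as combined better than alone better than sham, or as evidence that ICT adds benefit, when it shows neither. Two gaps make this worse:

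- **Sham level.** It either mixes earlier sham-plus-ICT patients with new sham patients who had no ICT, or uses the new sham only, which makes the contrast wholly between cohorts.
- **Study effect.** Nothing separates a treatment difference from a difference between 2017–2020 and 2021 onward.

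**Working it through.** The documents give no figure to reproduce for this analysis. The algebra below needs no assumed rates; the percentages do.

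**1. What the contrast estimates.** Let C, A and S be the log odds of relapse for combined, alone and sham.

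- Linear term: L = (C − S)/√2, with weights (+0.707, 0, −0.707).
- Quadratic term: Q = (C − 2A + S)/√6.
- Comparison promised in Section 4: C − A = 0.707·L + 1.225·Q.

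When both terms are fitted, A does not enter L. The promised comparison needs Q, or an explicit pairwise contrast, and neither is planned.

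**2. If only a linear score is fitted.** To first order, with similar variances, each group's weight is n(x − x̄), where x = +1, 0, −1.

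- At 30/30/30 (combined/alone/sham): x̄ = 0, so the middle weight is 0.
- At 60/30/90: x̄ = (60 − 90)/180 = −0.167. The weights are 70, 5 and −75, so the middle is 5/70 = 7% of the combined weight.
- At 60/30/30: x̄ = (60 − 30)/120 = 0.25. The weights are 45, −7.5 and −37.5, so the middle is 7.5/45 = 17% of the combined weight in size.

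The model also forces the two steps to be equal, so it cannot test either one.

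**3. Size.** Inputs: 60 patients in the new trial (Section 3.1), taken as 30 per arm because the ratio is not stated. Assumed: the earlier arm sizes, and 2-week relapse of 20% combined and 50% sham. The table shows the chance of a favourable significant result (Wald z below −1.96; 200,000 simulated trials per case).

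| Test, n combined/alone/sham | Alone 50% (useless without ICT) | Alone 35% | Alone 20% (ICT adds nothing) |
|---|---|---|---|
| Linear, quadratic also fitted, 30/30/30 | 68% | 68% | 68% |
| Linear, quadratic also fitted, 60/30/90 | 97% | 97% | 97% |
| Linear score only, 30/30/30 | 67% | 68% | 72% |
| Linear score only, 60/30/90 | 96% | 97% | 98% |
| Linear score only, 60/30/30 | 88% | 84% | 79% |
| Direct combined vs alone, 30 vs 30 | 68% | 23% | 2% |
| Direct combined vs alone, 60 vs 30 | 83% | 35% | 3% |

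Hand check of the first row: log OR = ln(0.25) = −1.386. SE = √(1/(30 × 0.16) + 1/(30 × 0.25)) = √(0.208 + 0.133) = 0.585. So z = −2.37 and power is Φ(2.37 − 1.96), about 66%, close to the simulated 68%.

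**4. Other assumed rates.** With 60% sham and 30% combined at 30 per group, the contrast is significant about 63% of the time when alone equals combined. With 50% and 35%, log OR = −0.619, SE = √(0.147 + 0.133) = 0.529, z = −1.17, and power is about 21%. The percentages move with the rates. With the quadratic fitted, the indifference to the middle group does not.

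**5. Specific and non-specific ICT as separate levels.** The weights become (0.67, 0.22, −0.22, −0.67). At 30 per level the chances are 89%, 79% and 62% for the three columns. The middle groups now count, but the test is still significant in most trials when ICT adds nothing.

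**6. Drift between studies with no treatment effect.** Assumed: relapse of 50% in the new trial, and 10, 15 or 20 points lower in the earlier one. A sound test gives about 2.5% favourable false positives.

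| Comparison | 10 points | 15 points | 20 points |
|---|---|---|---|
| Linear contrast, shams pooled | 6% | 9% | 13–14% |
| Linear contrast, new sham only | 12–14% | 22–28% | 35–46% |
| Ratio of within-study odds ratios | 2.5–2.7% | 2.5–2.7% | 2.5–2.7% |

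The ranges cover 30 and 60 combined patients. A direct combined-versus-alone contrast has the same exposure as the new-sham-only row, because it too compares 30 or 60 earlier patients with 30 new ones.

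**The case against.** The strongest reply is that a linear contrast is a recognised test against an ordered alternative, and the plan does not say that it will be read as proof of each step. If the levels are fitted as a factor, the combined-versus-alone estimate can be recovered from the same model. The question in Section 1 is answered mainly by the randomised comparison. Section 2 lists no ICT hypothesis, and the promise sits in the Benefits section. The study also keeps the same tDCS configuration and "takes place within the same multidisciplinary framework of treatment in order to compare our data".

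Parts of this stand. The pooled data could yield the comparison; the fault lies in the contrast that was chosen. The randomised active-versus-sham regression does test whether tDCS works without ICT, so the harm is confined to the cross-study conclusion. In a slope-only model with 60/30/30 the middle arm moves the result by about 10 points (88% to 79%), so its influence is not always negligible. The main percentages rest on one assumed pair of rates, and a direct combined-versus-alone contrast is just as exposed to drift.

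None of this supplies the missing test. The model that could give the pairwise estimate is not the analysis stated. Even at 60/30/30 the contrast is significant in 79% of trials when ICT adds nothing. A shared setting helps comparability but does not remove a difference between periods.

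**Conclusion.** The point holds and should be fixed. As written, the only analysis that includes the combined arms does not test tDCS alone against tDCS plus ICT. For three equally spaced levels with the quadratic fitted, that is exact and needs no assumed rates. For a slope-only model it holds closely. Under the assumed 20% and 50% relapse, the contrast reaches significance about as often when ICT adds nothing as when tDCS is useless without it: 68% and 68% with the quadratic fitted, 72% and 67% with the slope only, at 30 per level.

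The earlier arm sizes, all relapse rates and the amount of drift are assumptions, because the documents give none. A smaller effect lowers every percentage. The new trial's own randomised comparison stands.

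**What to change.** Replace the linear contrast with two pre-specified comparisons, each reported as an odds ratio or ratio of odds ratios with a 95% CI:

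1. tDCS alone versus sham within the new trial (randomised, already planned).
2. The tDCS effect with versus without ICT, as the ratio of the two within-study active-versus-sham odds ratios. Use a logistic model with study, tDCS and study × tDCS; with 0/1 coding, the exponentiated interaction is this ratio.

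State how the six conditions map: for example, both earlier active arms as combined, each study's sham as its own control, and specific ICT also shown separately. Label comparison 2 exploratory and non-randomised. ICT stays confounded with study, and the ratio shows whether the effect of tDCS over sham differs, not the total benefit of adding ICT.

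Reword the Section 4 sentence, for example: *It will explore, by a non-randomised comparison with our previous study, whether the effect of tDCS differs with and without cognitive training.*

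The change is wording and a short model, with no new data. The price is precision. At the assumed rates with 30 per arm and alone at 50%, SE = √(0.208 + 3 × 0.133) = 0.780. The 95% CI then spans a factor of exp(1.96 × 0.780) = 4.6 either side, or 5.1 if alone is at 20%, against 3.1 for combined versus new sham. With 60 combined and 60 earlier sham patients the factors are 3.7–4.1 against 2.6. Even if tDCS alone were useless, power would be about 43%, or 55% with the larger earlier groups. The result will often be inconclusive, and the plan should say so.

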3. PROTOCOL

3.1. Patients

This is a clinical trial that is part of an alcohol detoxification cure at Unit 72 Addictology of CHU Brugmann. The idea is to add a neuromodulation intervention to the initial management, multidisciplinary and psycho-bio-social. This will be a randomized, sham-controlled, single-blind study.

A total of 60 subjects will be recruited according to the inclusion and exclusion criteria. They will be randomly divided into two groups: the 'active' group (A) that will benefit from tDCS stimulation and the 'sham' group (S).

Exclusion criteria:

- Personal history of epilepsy;
- Have metal head implants that counter-indicate electrical stimulation;
- Diagnosis of chronic psychotic disorder, schizophrenia or bipolar type 1 disorder;
- Use of alcohol or other illicit substances during the experiment;
- Hair incompatible with neuromodulation.

[figure not shown]

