3.2. Procedure

During the first two weeks of hospitalization, the study will be offered to patients. If they accept, a first semi-structured interview will be organized to explain the study, sign the informed consent, collect more information and verify the inclusion and exclusion criteria. During this interview, the demographic characteristics (age, sex and level of education), history with alcohol (number of years of dependence, number of previous treatment, etc.), frequency and amount of alcohol consumed before treatment, psychiatric history, etc. The DSM 5 criteria will be verified, and patients will complete these questionnaires in French version: *Alcohol Use Disorder Identification Test (AUDIT)*, *Impulsivity Behavior Scale (UPPS-P)* and *Trait Anxiety Inventory (STAI-B)*.

From Monday to Friday of the third week of hospitalization, patients will receive the procedure. Five consecutive 20 minute days of tDCS, either active or sham. Before and after each session, the tie will be measured using analog visual scales. To measure the effects of tDCS, on the Friday preceding (T1) and the Monday following (T2) the intervention week,

patients will respond to a battery of questionnaires and cognitive tasks during the recording of evoked potentials (via an electroencephalogram). T1 and T2 will each last approximately one hour.

Figure 1: Study plan. Day 1 is theoretically the first day of hospitalization and the procedure takes place between Day 15 and 19.

In order to observe whether specific neural changes underlie relapse and abstinence, evoked potentials will be acquired for each participant at two points, before the start of the stimulation by tDCS and once the five sessions have been completed.

Once hospitalization is complete, patients will be followed by telephone call to find out the status of their abstinence and/or alcohol consumption. The call will be made via Unit 72 personnel.

Recruitment would start if possible at the end of March 2021 for a period of 12 months. Based on our estimates based on the performance of the previous study, five patients will be recruited per month.

[figure not shown]
3.3. tDCS

During the neuromodulation session, the patient will watch nature documentaries, cut into 5 episodes of 20 minutes.

The configuration of tDCS is based on recommendations in the literature (Fregni et al., 2020; Lefaucheur et al., 2017).

- 5 sessions of bilateral stimulation of the dlPFC;

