3.4. Measures

Primary dependent variables :

Relapse and total abstinence measured at several defined times: two weeks, one month, three months, six months and one year after treatment..

Secondary dependent variables:

- Craving measured before and after each tDCS session via visual analog scales, such as Likert -100 to +100, as well as the *Alcohol Urge Questionnaire* (AUQ) with 8 items. Craving will also be measured in T1 and T2 through the *Craving Experience Questionnaire* (CEQ);

- Symptoms of depression with the *Beck Depression Inventory* (BDI-II) and positive and negative affectivity with the Positive and Negative Affect Schedule (PANAS) measured at T1 and T2;
- Anxiety trait in T1 and T2 with the *State Anxiety Inventory* (STAI-A).
- The working memory performance measured in T1 and T2 with the span reversed.
- Inhibitory control evaluated by performance at a Go/Nogo task and its event-related potential (Nogo N2 and Nogo P3). This measurement will be carried out as part of a clinical examination (cognitive and neurophysiological battery with an electroencephalogram) offered to patients during their hospitalization at Unit 72. This review will be conducted before and after the intervention (in T1 and T2).

All the questionnaires were in French version.

Metacognition items:

At the end of the experiment, patients will be asked orally (1) Do you think you are in the active tDCS group?, (2) Would you be interested in continuing this intervention over a longer period of time?

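### The T1/T2 repeated-measures ANOVA for the secondary outcomes drops every patient without a T2 visit, and the plan makes no provision for such patients; the gap is clearest for Go/Nogo with evoked potentials

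*Combined protocol and SAP*

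**What the plan says.** Section 3.5 gives one method for all before/after secondary outcomes: "we will perform mixed repeated measures ANOVAs [Time (T1 vs. T2) x Condition (tDCS active vs. tDCS sham"). It says nothing about patients with only one of the two visits. The document defines no analysis set, expected loss, missing-data method or sensitivity analysis.

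Section 3.2 fixes the visits by calendar, "on the Friday preceding (T1) and the Monday following (T2) the intervention week". The appendix table puts them at Day 12 and Day 22, with the sessions on Days 15 to 19. For the evoked potentials, section 3.2 adds that the two recordings are made "before the start of the stimulation by tDCS and once the five sessions have been completed", and it plans them for each participant. Section 3.4 places the Go/Nogo and evoked-potential measure within a "clinical examination (cognitive and neurophysiological battery with an electroencephalogram) offered to patients during their hospitalization at Unit 72". BDI-II, PANAS, STAI-A and the reverse span are simply scheduled at T1 and T2.

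On size, section 3.1 says "A total of 60 subjects will be recruited according to the inclusion and exclusion criteria" and "They will be randomly divided into two groups", without an allocation ratio.

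**The concern.** Three of the four hypotheses in section 2 (craving, depression and anxiety, inhibition) rest on this test. Between T1 and T2 lie ten days of inpatient detoxification with five daily sessions, so some missing T2 visits are plausible. Section 3.1 also lists substance use during the experiment as an exclusion criterion. If that is applied after randomisation, it removes patients for a reason close to the outcome.

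Suppose patients with high T1 craving leave more often in one arm than in the other. The completers then start from different T1 levels, and regression to the mean alone makes their average change differ between arms when tDCS has no effect. The result can be a false effect or a masked one. T2 data that were never collected cannot be recovered at analysis.

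**Working it through.** **The plan's own figure.** Section 3.2 says "Recruitment would start if possible at the end of March 2021 for a period of 12 months" and "five patients will be recruited per month". That gives 5 × 12 = 60, which reproduces the sample size. It is an accrual forecast with no allowance for loss. To end with 60 patients who have T2, enrolment would be 60/0.9 = 67, 60/0.8 = 75 or 60/0.7 = 86 at 10%, 20% or 30% loss, rounding up.

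**Assumptions, none given in the documents.** 30 patients per arm; T1 and T2 standardised with correlation ρ = 0.4 or 0.6; no treatment effect; a share p of each arm missing at T2. In sham, leaving is correlated r = 0.8 with T1 (the highest values leave). In active, it is unrelated to T1.

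**Bias of the completers' test.** With λ(p) = φ(z)/(1 − p), where z is the normal quantile at 1 − p, the sham completers' mean T1 is −rλ(p) and their mean T2 is −ρrλ(p). Their mean change is therefore (1 − ρ)rλ(p), against 0 in active.

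- p = 0.1: λ = 0.1755/0.9 = 0.195, rλ = 0.156
- p = 0.2: λ = 0.2800/0.8 = 0.350, rλ = 0.280
- p = 0.3: λ = 0.3477/0.7 = 0.497, rλ = 0.397

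The standard error is √[2(1 − ρ)] × √(1/n_active + 1/n_sham). Normal-approximation results for ρ = 0.6 and ρ = 0.4:

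| Loss active/sham | T2 completers | Bias (SD) | Bias/SE | Type I error |
|---|---|---|---|---|
| 10%/10% | 27/27 | 0.06, 0.09 | 0.26, 0.31 | 5.8%, 6.1% |
| 20%/20% | 24/24 | 0.11, 0.17 | 0.43, 0.53 | 7.2%, 8.3% |
| 10%/30% | 27/21 | 0.16, 0.24 | 0.61, 0.75 | 9.4%, 11.6% |

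With symptom scores where higher is worse, this bias favours active tDCS. Simulated trials of 30 per arm agree: 0.06 to 0.10, 0.11 to 0.17 and 0.15 to 0.23 SD, with type I errors of 5.7 to 6.4%, 7.2 to 8.4% and 9.1 to 11.3%. A likelihood estimate that keeps T1-only patients has bias of about 0.01 SD or less in these scenarios.

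**Same mechanism, different rates.** With the same r in both arms and 10%/30% loss, the bias is (1 − ρ)r(0.497 − 0.195). This runs from 0.4 × 0.5 × 0.302 = 0.06 to 0.6 × 0.8 × 0.302 = 0.14 SD. With weaker, logistic dependence on T1 and ρ of 0.5 to 0.7, simulation gave 0.05 to 0.09 SD at 10%/30% and 0.08 to 0.13 SD at 5%/30%.

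**Same mechanism, same rate.** The two arms' terms cancel. Simulation at 20%/20% gave a bias of at most 0.003 SD in absolute value. Only precision is lost: for an assumed 0.5 SD effect and ρ = 0.5, power falls from 49% to 45%, 41% or 37% at 10%, 20% or 30% loss.

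**Other mechanisms (loss related in sham only, r = 0.8).**

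- Loss depends on T2. The completers' bias has the same size, (1 − ρ)rλ, with opposite sign. The likelihood estimate's bias is about (1 − ρ²)rλ: from 0.64 × 0.156 = 0.10 to 0.84 × 0.397 = 0.33 SD, so it is larger.
- Loss depends on the overall level T1 + T2. With equal variances this sum is uncorrelated with T2 − T1, so the completers' test is essentially unbiased (at most 0.007 SD in simulation). The likelihood estimate is biased by 0.06 to 0.22 SD.

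**The case against.** A reader might infer that a patient who stops sessions is barred from T2 for every secondary outcome. The documents do not support that. The five-session wording is attached to the evoked potentials, and the word for an offered examination to Go/Nogo with evoked potentials; the questionnaires and the span task follow the calendar. Even for the EEG, the five-session phrase can be read as timing and not as a rule against non-completers, since section 3.2 plans recordings for each participant and section 3.4 says the examination takes place at T1 and T2. What stands is that the text can be read either way and that no sentence says what happens at T2 to a patient who stopped early.

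The plan also never states that it analyses complete cases only. That follows from how the method usually works and from the plan's silence.

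A second tempting reading is that a mixed model removes the problem. It does so when missingness depends only on T1 and arm. The account of patients leaving during the stimulation week because of high craving or low mood points partly to their state after T1, and there the mixed model can be worse than the planned test. This objection stands and shapes the fix.

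Finally, the sizes are assumed throughout, and the upper values need strong dependence in one arm and none in the other. These are secondary outcomes; the relapse analysis is not affected by this point.

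**Conclusion.** The point holds in a limited form. The planned test uses only patients with both visits, and the plan does not provide for the others. The exposure is clearest for Go/Nogo with evoked potentials, the only measure of the inhibition hypothesis. For craving, mood and anxiety it is confined to patients who miss Day 22.

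Bias in Time × Condition arises when loss differs between arms in rate or mechanism. Under the assumed T1-related loss it is about 0.06 to 0.24 SD, with type I error of about 6 to 12%; with the same rate and mechanism in both arms it is about zero. Because the documents give no T2 loss rate, these figures show what could happen and do not predict it. It would be wrong to conclude that the ANOVA result will be biased, or that one method is less biased under every mechanism. The change should be made, at medium confidence, mainly because it is cheap and uncollected T2 data cannot be replaced.

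**What to change.** 1. In sections 3.2 and 3.4, state that the T2 battery, including Go/Nogo with evoked potentials, is done on the planned Monday for every randomised patient still present, whatever number of sessions was received. This reduces missing data under any mechanism and is the most valuable part.
2. In section 3.5, analyse each T1/T2 outcome with a linear mixed model (Time, Condition, Time × Condition, unstructured covariance, REML) that includes every randomised patient with a T1 or T2 value, with the interaction as the test. With complete data this test is equivalent to the planned ANOVA.
3. Keep the complete-pair ANOVA as a sensitivity analysis, and add a delta-adjusted analysis in which missing T2 values are shifted by a stated range, separately by arm, because the mixed model's assumption cannot be checked from the data.
4. Reconcile the Craving Experience Questionnaire schedule: section 3.4 has it at T1 and T2, the appendix table at the interview only. Under the table it could not enter this analysis for anyone.

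The cost is protocol and SAP wording, a few extra T2 visits and slightly more analysis. The mixed model still relies on missingness depending only on T1 and arm.
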